4.3 Exploratory Efficacy Endpoints

The exploratory efficacy endpoints are as follows:

1. Change from baseline in Fugl-Meyer Motor Scale (FMMS) score at Week 24 among patients with both upper and lower extremity deficits
2. Change from baseline in Fugl-Meyer Motor upper-extremity subscale (UE-FM) score at Week 24 among upper extremity deficit patients
3. Change from baseline in Fugl-Meyer Motor lower-extremity subscale (LE-FM) score at Week 24 among lower extremity deficit patients
4. Improvement by ≥ 6 points at Week 24 from Baseline in UE-FM score among upper extremity deficit patients
5. Improvement by ≥ 3 points at Week 24 from Baseline in LE-FM score among lower extremity deficit patients
6. Improvement from Baseline by ≥ 10 points at Week 24 in Fugl-Meyer Motor Scale (FMMS) score among all patients
7. Improvement from Baseline by ≥ 6 points at Week 24 in Action Research Arm Test (ARAT) score among upper extremity deficit patients
8. Improvement from Baseline of at least one functional level [e.g., from < 0.4 m/s to $0.4-0.8$ m/s or from $0.4 - 0.8$ m/s to > 0.8 m/s] at Week 24 in Gait Velocity on standard 10 m walk among lower extremity deficit patients
9. Pre- and post-contrast standard T1 and T2 weighted, dual echo, and FLAIR-MRI among all patients
10. Perfusion MRI among all patients
11. Diffusion tensor imaging (DTI) with tractography among all patients
12. Lower limb motion as measured by leg activity monitor among lower extremity deficit patients (applicable for US and Japan only)
13. Outcome analysis among all patients based on genotyping of polymorphisms at 3 specific loci:
 - HLA – degree of donor/recipient mismatch
 - BDNF Val66Met mutation present (yes/no)
 - ApoE (i.e., homo and heterozygosity for ApoE2, ApoE3, ApoE4 alleles)

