	 Change from baseline in T scores at Week 24 of NeuroQOL Domains: 						
	 Upper Extremity Function (Fine motor ADL) among upper extremity deficit patients 						
	 Lower Extremity Function (Mobility) among lower extremity deficit patients 						
	• Global Rating of Perceived Change scores at Week 24 (from baseline) among all patients: assessed by the subject (may be completed by caregiver) and by the clinician						
	For the mITT Population, patients with a Motricity Index UE Scale score at Screening of 10-81 will be considered to have an upper extremity deficit, and patients with a LE Scale score at Screening of 10- 78 will be considered to have a lower extremity deficit. For the Per Protocol Population, patients with a Motricity Index UE Scale score at Screening of 10-81, at least two scores less than 33 with one of these less than 25, and at least one score greater than 0, will be considered to have an upper extremity deficit, and patients with a LE Scale score of 10-78, at least two scores less than 33 with one of these less than 25, and at least one score greater than 0, will be considered to have a lower extremity deficit.						
Safety	• All adverse events whether or not related to SB623 or the surgical						
Parameters	procedure using WHO toxicity criteriaAdverse changes imaged by head MRI						
	 Adverse changes imaged by head MRI Serious adverse events (SAEs) using WHO toxicity criteria 						
	 Serum chemistry, hematology, vital signs, physical examinations 						
	 Serum chemistry, hematology, vital signs, physical examinations Changes in serum antibodies to SB623 over time 						

SanBio, Inc.	Confidential and Proprietary
Exploratory	Change from baseline in Fugl-Meyer Motor Scale (FMMS) score at
Endpoints &	Week 24 among patients with both upper and lower extremity deficits
Analyses	Change from baseline in Fugl-Meyer Motor upper-extremity subscale
	(UE-FM) score at Week 24 among upper extremity deficit patients
	Change from baseline in Fugl-Meyer Motor lower-extremity subscale
	(LE-FM) score at Week 24 among lower extremity deficit patients
	• Improvement by ≥ 6 points at Week 24 from Baseline in UE-FM score
	among upper extremity deficit patients
	• Improvement by \geq 3 points at Week 24 from Baseline in LE-FM score
	among lower extremity deficit patients
	• Improvement by ≥ 10 points at Week 24 from Baseline in Fugl-Meyer
	Motor Scale (FMMS) score among patients with both upper and lower extremity deficits

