5.2.3 Exploratory Endpoints

- Change from baseline in Fugl-Meyer Motor Scale (FMMS) score at Week 24 among patients with both upper and lower extremity deficits
- Change from baseline in Fugl-Meyer Motor upper-extremity subscale (UE-FM) score at Week 24 among upper extremity deficit patients
- Change from baseline in Fugl-Meyer Motor lower-extremity subscale (LE-FM) score at Week 24 among lower extremity deficit patients
- Improvement by ≥6 points at Week 24 from Baseline in UE-FM score among upper extremity deficit patients
- Improvement by ≥3 points at Week 24 from Baseline in LE-FM score among lower extremity deficit patients
- Improvement by ≥10 points at Week 24 from Baseline in Fugl-Meyer Motor Scale (FMMS) score among patients with both upper and lower extremity deficits
- Improvement by ≥6 points at Week 24 from Baseline in Action Research Arm Test (ARAT) score among upper extremity deficit patients
- Improvement of at least one functional level [e.g., from <0.4 m/s to 0.4-0.8 m/s or from 0.4 0.8 m/s to >0.8 m/s] at Week 24 from Baseline in Gait Velocity on standard 10 m walk among lower extremity deficit patients

Pre- and post-contrast standard T1 and T2 weighted, dual echo, and FLAIR-MRI among all patients

- Diffusion tensor imaging (DTI) with tractography among all patients
- Perfusion MRI among all patients
- Lower limb motion as measured by leg activity monitor among lower extremity deficit Patients (applicable for US and Japan only)
- Outcome analysis among all patients based on genotyping of polymorphisms at 3 specific loci:
 - HLA degree of donor/recipient mismatch
 - BDNFVal66Met mutation present (yes/no)
 - ApoE (*i.e.*, homo and heterozygosity for ApoE2, ApoE3, ApoE4 alleles)

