7.0 PATIENT SELECTION

7.1 Inclusion Criteria

- 1. Age 18-75 years
- 2. Documented history of TBI, with correlated MRI or CT
- 3. At least 12 months post-TBI
- 4. Focal cerebral injury able to be identified on MRI (+/- concomitant diffuse axonal injury)
- 5. Neurological motor deficit substantially due to focal cerebral injury observed on MRI
- 6. GOS-E score of 3-6 (i.e. moderate or severe disability)
- 7. Require Motricity Index UE Scale of 10-81, at least two scores less than 33 with one of these less than 25, and at least one score greater than 0, and/or a LE Scale of 10-78, at least two scores less than 33 with one of these less than 25, and at least one score greater than 0.
- 8. Able and willing to undergo computed tomography (CT) and magnetic resonance imaging (MRI)
- 9. Must agree to use of antiplatelet, anticoagulant, or non-steroidal anti-inflammatory drugs to be in accordance with the Anticoagulant Guidelines described in Appendix C.
- 10. Subjects must be willing to participate in study related exercises to the extent possible
- 11. Must be willing to discontinue herbal or non-traditional medicines for 1 week before and 1 week after the surgical procedure
- 12. Able to undergo all planned neurological assessments
- 13. Ability of patient to understand and sign an Informed Consent

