20.1 Justification for use of the Fugl-Meyer Motor Scale as primary endpoint

The Fugl-Meyer (F-M) scale was developed specifically because prior scales focused on Activities of Daily Living (ADLs) and measures of global function and not on specific improvements in the neuromuscular function of the affected limb. The need that gave rise to the F-M scale was for a specific and quantitative method for measuring recovery from hemiplegia.¹¹ The F-M scale is now one of the most widely recognized and clinically relevant measures of body function impairment.¹² The motor component of the F-M scale in particular has well-established reliability and validity across different recovery time points.^{11, 13}

The F-M scale assesses several dimensions of impairment, including range of motion, pain, sensation, upper extremity, lower extremity, and balance.¹⁴ The items of the F-M are mainly scored on a 3-point Likert-type ordinal scale, from 0 to 2 applied to each item, and the items are summed to provide a maximum score of 226. The motor domain includes items measuring movement, coordination, and reflex action about the upper extremity joints (shoulder, elbow, forearm, wrist, hand) and lower extremity joints (hip, knee, and ankle). The motor score ranges from 0 (hemiplegia) to a maximum of 100 points (normal motor performance).¹¹ The F-M motor component consists of the 33-item upper-extremity subscale (UE- FM) and the 17-item lower-extremity subscale (LE-FM).¹⁴ The UE-FM ranges from 0 to 66¹⁵ and the LE-FM from 0-34. The use of these subscales can be used alone to lessen the patient burden of the full questionnaire.

The F-M scale assesses several impairment dimensions and has been extensively used in studies with **chronic** motor deficit following neurological injury. In fact, in a systematic review of RCTs examining robot assisted therapy, 60% of the RCTs included in analysis used the F-M scale as the primary outcome parameter.¹⁶ More recent RCTs investigating the use of patients continue to use the F-M motor scale as the primary outcome measure.¹⁷⁻²⁰ Other studies include constraint induced therapy trials^{21, 22}, brain-machine interface²³, transcutaneous electrical nerve stimulation (primary outcome measure)^{24, 25} and mirror therapy (primary outcome measure in this 33 patient RCT).²⁶

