3.5 Changes to the Protocol-Specified Analyses

An As Treated Population was added to the analysis populations.

The protocol stated that a mixed model repeated measures (MMRM) analysis with terms for treatment, visit, the baseline Fugl-Meyer Motor Scale score, the GOS-E score at screening, and the treatment-by-visit interaction would be performed for the primary efficacy endpoint. The model has been revised to now include terms for the baseline Fugl-Meyer Motor Scale score-by-visit interaction and the GOS-E score at screening-by-visit interaction.

The protocol stated that the following secondary efficacy endpoints would be analyzed in a manner analogous to that for the primary efficacy endpoint: the change from baseline in the Disability Rating Scale (DRS) score at Week 24, the change from baseline in the Action Research Arm Test (ARAT) total score at Week 24, the change from baseline in Gait Velocity at Week 24, and the change from baseline at Week 24 in the two NeuroQOL subdomain T scores (Upper Extremity Function (Fine Motor ADL) and Lower Extremity Function (Mobility)). Thus, the protocol specified model did not include terms for the baseline value of the endpoint-by-visit interaction or the GOS-E score at screening-by-visit interaction. These terms were added to the model for each of these endpoints.

The protocol stated that the primary efficacy endpoint and each of the above mentioned secondary efficacy endpoints would be analyzed to examine dose response, and that similar statistical methodology to that used to evaluate the SB623 combined doses vs. the sham surgery control treatment would be used, except that dose would be used instead of treatment and dose would be a continuous variable with the control treatment assigned a value of 0. Instead the MMRM analysis will be performed using a model with terms for visit, the interaction between SB623 dose and an indicator variable for the Week 4 visit, the interaction between SB623 dose and an indicator variable for the Week 12 visit, the interaction between SB623 dose and an indicator variable for the Week 24 visit, the baseline value of the endpoint, the baseline value of the endpoint-by-visit interaction, the GOS-E score at screening, and the GOS-E score at screening-by-visit interaction. The control treatment will not be included in this analysis.

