4.0 EFFICACY AND SAFETY ENDPOINTS

For the mITT Population (see Section 6.1), patients with a Motricity Index UE Scale score at Screening of 10-81 will be considered to have an upper extremity deficit. Patients with a LE Scale score at Screening of 10-78 will be considered to have a lower extremity deficit. For the Per Protocol Population (see Section 6.2), patients with a Motricity Index UE Scale score at Screening of 10-81, at least two scores less than 33 with one of these less than 25, and at least one score greater than 0, will be considered to have an upper extremity deficit. Patients with a LE Scale score at Screening of 10-78, at least two scores less than 33 with one of these less than 25, and at least one score greater than 0, will be considered to have a lower extremity deficit.

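### The SAP widens the exploratory 10-point FMMS responder endpoint from patients with both upper and lower extremity deficits to all patients, and its list of changes does not say so

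*SAP*

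**What the plan says.** Protocol section 5.2.3 defines response as a gain of at least 10 "points at Week 24 from Baseline in Fugl-Meyer Motor Scale (FMMS) score among patients with both upper and lower extremity deficits". The synopsis has the same restriction: "Motor Scale (FMMS) score among patients with both upper and lower extremity deficits". The same list gives a 6-point threshold on the arm subscale (UE-FM) for patients with an upper extremity deficit, and a 3-point threshold on the leg subscale (LE-FM) for those with a lower extremity deficit.

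The SAP (Appendix A, section 4.3, item 6) keeps the 10 points but counts "points at Week 24 in Fugl-Meyer Motor Scale (FMMS) score among all patients". Section 10.3 repeats this and assigns the endpoint to a logistic regression on treatment, the baseline value and GOS-E.

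SAP section 3.5 is headed as the list of changes to protocol-specified analyses. It opens with "An As Treated Population was added to the analysis populations" and then covers the added covariate-by-visit terms and the revised dose-response model. It mentions no exploratory endpoint, and neither does the addendum.

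**The concern.** A change list tells the reader of the study report which results follow the protocol and which do not. Here the population of a protocol-defined endpoint changed, each document is consistent with itself, and the list is silent. A reader who relied on section 3.5 would take the all-patient responder rate to be the protocol's endpoint. The both-deficit rate would not be reported at all. The endpoint is exploratory, so what is at stake is traceability and one missing result, not the trial's main conclusion.

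**Working it through.** **1. Is this a stray slip?** The protocol restricts the population in two places (synopsis, 5.2.3). The SAP says all patients in two places (4.3, 10.3). Item 1 of the same SAP list, the mean FMMS change, keeps the both-deficits restriction. Only the responder item was widened.

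**2. Do the two populations differ?** Yes. The Motricity Index criterion in protocol section 7.1 joins the two extremities with and/or: "and at least one score greater than 0, and/or a LE Scale of 10-78". One qualifying extremity is therefore enough. For the mITT population, SAP section 4.0 defines deficit by a score range: "patients with a Motricity Index UE Scale score at Screening of 10-81 will be considered to have an upper extremity deficit", and 10-78 for the leg. The all-patient set therefore adds patients whose second extremity scores above its range, and also any whose second extremity scores below 10.

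**3. How do the thresholds relate to the scales?** Protocol section 20.1 gives 0-100 for the motor score, 0-66 for UE-FM, "and the LE-FM from 0-34".

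- Protocol thresholds: 10/100 = 10.0%; 6/66 = 9.1%; 3/34 = 8.8%.
- Sum of the two limb thresholds: 6 + 3 = 9 points.
- If the whole gain had to come from one limb: 10/66 = 15.2% of the arm range, or 10/34 = 29.4% of the leg range.

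The pairing of thresholds with populations looks deliberate, but no derivation of the 10 points is given.

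**4. Does the plan give a figure for this endpoint?** No. The nearest is the sample size for the primary endpoint (SAP 3.4), which reproduces: control n = (1 + 1/3) x (1.960 + 0.842)^2 x 7.25^2 / 7^2 = 11.2, rounded up to 12, so 48 in total at 3:1. Exact t-test power at 36:12 is 80.9%.

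**5. Could the size of the effect be worked out?** Only under assumptions that the documents do not make. As an illustration, take normal changes and apply the planning values (means 10.0 and 3.0, SD 7.25) to both-deficit patients:

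- SB623: 1 - Phi((10 - 10)/7.25) = 50.0%.
- Sham: 1 - Phi((10 - 3)/7.25) = 16.7%.
- Difference: about 33 points.

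Let one-limb patients' mean changes shrink to that limb's share of the scale (0.66 arm, 0.34 leg), with the SD either unchanged or shrunk likewise. For leg-only patients with SD 7.25, the rates are 1 - Phi((10 - 3.4)/7.25) = 18.1% and 1 - Phi((10 - 1.02)/7.25) = 10.8%, a difference of about 7 points. The table mixes the groups. Each range covers arm-only or leg-only patients under either SD. Power is Phi[(difference - 1.96 x pooled SE)/unpooled SE], with 13 sham and 39 SB623 patients in total (52 at 3:1) and the both-deficit subset split 3:1.

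| Assumed one-limb share | All-patient difference (points) | Power, all patients | Power, both-deficit only |
|---|---|---|---|
| 10% | 30 to 32 | 49 to 54% | 52% |
| 25% | 25 to 30 | 37 to 49% | 44% |
| 50% | 17 to 26 | 20 to 41% | 29% |

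Under these assumptions the wider population dilutes the difference, but its power may be higher or lower than that of the restricted one. If one-limb patients gained as much as the others, there would be no dilution.

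**The case against.** The best defence is that an all-patient version is reasonable. Ten points is 10% of the 100-point motor scale, and protocol section 3.3 treats a gain of 10% of scale range as clinically important. Ten is also the mean gain assumed for SB623 on a primary endpoint that covers all patients. This stands as a reason to keep the all-patient version as an addition. It does not explain why the change was left unlisted.

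A second defence is procedural. Protocol section 18.2.2.3 leaves exploratory analyses to the SAP, and section 18.8 requires departures to be described in the study report. However, section 5.2.3 had already fixed the population, and a change missing from SAP section 3.5 is easily missed in the report.

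A third is that related results are planned: the two limb responder endpoints, the mean FMMS change in both-deficit patients, and cumulative distribution curves (SAP 10.4). These help, but the FMMS curve is for all patients, so none of them gives the both-deficit 10-point rate.

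A reader might go further and infer three things that the documents do not support:

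- **That a two-limb threshold is being misapplied to one-limb patients.** The origin of the 10 points is not stated. Disagreement between limb and total response also occurs in the protocol's own population: gains of 6 and 3 meet both limb thresholds but total 9. The 29.4% figure needs the whole gain to come from the leg, yet a patient without an mITT arm deficit may have an arm scoring below 10, with room to improve.
- **That chance imbalance in the one-limb mix is likely to distort the comparison.** Randomisation is not stratified by limb involvement, but no prevalence is given, and the baseline FMMS score in the model may capture part of it.
- **That the small sham group makes the wider population fragile.** One of about 13 sham patients is 1/13 = 7.7 points in any binary endpoint. Restricting the population cannot make that weight smaller and would probably increase it.

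**Conclusion.** The mismatch and its absence from section 3.5 are certain on the text. The consequence is limited: one protocol-defined exploratory responder rate would go unreported, and the change list is incomplete. No claim about bias, or about a wrong threshold, can be added. The size and direction of any effect depend on the share of one-limb patients and on their gains, neither of which the documents give; the table above is an illustration, not an estimate. The primary and secondary analyses and the sample size are untouched. This is a minor point, worth correcting because the correction is so cheap.

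**What to change.** In SAP sections 4.3 and 10.3, item 6, report the 10-point responder endpoint in patients with both upper and lower extremity deficits, using the section 4.0 deficit definitions for the mITT and Per Protocol populations. If the all-patient version is also wanted, label it an additional analysis and list it in section 3.5 with the reason.

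The work is a wording change, one population flag and one line in section 3.5. The drawback is fewer patients in the protocol-population table, plus one extra table if both versions are kept. Little is lost if only the protocol version is tabulated, because the planned all-patient FMMS distribution curve already shows the unadjusted all-patient rate at 10 points.

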4.4 Safety Endpoints

The safety endpoints are as follows:

- All adverse events whether or not related to SB623 or the surgical procedure using WHO toxicity criteria
- Adverse changes imaged by head MRI
- Serious adverse events (SAEs) using WHO toxicity criteria
- Serum chemistry, hematology, vital signs, and physical examination
- Changes in serum antibodies to SB623 over time

5.0 STATISTICAL CONSIDERATIONS

5.1 General Methodology

The statistical analysis of the data obtained from this study will be performed using SAS[®] version 9.4 or higher. All statistical tests will be performed at the 0.05 significance level.

The data collected in this study will be documented using summary tables and subject data listings. Continuous variables will be summarized using descriptive statistics, specifically the number of observations, mean, median, standard deviation, minimum and maximum. Categorical variables will be summarized by frequencies and percentages. For the most part results will be presented for the four treatment groups separately and the three SB623 dose groups pooled. The three SB623 dose groups will be pooled for all statistical tests comparing SB623 to sham surgery, except where noted otherwise (i.e., dose response analyses).

Data listings will be sorted by center and subject ID. All date fields will be presented in a format of ddmmmyyyy (i.e., 01Jan2018) in the listings.

5.2 Adjustments for Covariates

A mixed model repeated measures (MMRM) analysis with adjustment for the baseline value of the endpoint and the GOS-E score at screening as continuous covariates as well as the corresponding baseline-by-visit and GOS-E score at screening-by-visit interaction terms will be used to analyze the following endpoints:

- The primary efficacy endpoint, the change from baseline in the Fugl-Meyer Motor Scale (FMMS) score at Week 24 among all patients
- Change from baseline in the Disability Rating Scale (DRS) score at Week 24 among all patients
- Change from baseline in the Action Research Arm Test (ARAT) total score at Week 24 among upper extremity deficit patients
- Change from baseline in Gait Velocity at Week 24 among lower extremity deficit patients
- Change from baseline at Week 24 in the two NeuroQOL subdomain T scores (Upper Extremity Function (Fine Motor ADL) and Lower Extremity Function (Mobility)) among upper and lower extremity deficit patients, respectively
- Change from baseline in Fugl-Meyer Motor Scale (FMMS) score at Week 24 among patients with both upper and lower extremity deficits
- Change from baseline in Fugl-Meyer Motor upper-extremity subscale (UE-FM) score at Week 24 among upper extremity deficit patients
- Change from baseline in Fugl-Meyer Motor lower-extremity subscale (LE-FM) score at Week 24 among lower extremity deficit patients.

The endpoints mentioned above will be analyzed to examine dose response using a MMRM model with adjustment for the baseline value of the endpoint and the GOS-E score at screening as continuous covariates as well as the corresponding baseline-by-visit and GOS-E score at screening-by-visit interaction terms.

The primary efficacy endpoint will also be analyzed using an analysis of covariance model with adjustment for the presence of prior (i.e., at baseline) antibodies to donor cell HLA antigens, the interaction between treatment and the presence of prior antibodies to donor cell HLA antigens, the baseline FMMS score, and the GOS-E score at screening.

The proportions of SB623 treated subjects (pooling all SB623 doses) scoring either 7 (much better) or 6 (a little better, meaningful) on the Global Rating of Perceived Change (from Baseline) - Subject at Week 24 and on the Global Rating of Perceived Change (from Baseline) - Clinician at Week 24 will be compared to the corresponding proportions of sham surgery control subjects using logistic regression models with adjustment for the baseline Fugl-Meyer Motor Scale score and the GOS-E score at screening as continuous covariates.

The fourth, fifth, sixth, seventh, and eighth exploratory efficacy endpoints will be summarized using frequencies and percentages and will be analyzed using a logistic regression model with adjustment for the baseline value of the endpoint and the GOS-E score at screening as continuous covariates.

